Patency and limb salvage are the primary measures for revascularization success in CLI patients. Primary and secondary patency rates at one year are significantly lower with endovascular compared with open surgical techniques, while limb salvage rates are similar in both groups (Romiti et al., 2008). Table 2. shows results from a meta-analysis comparing endovascular versus open bypass outcomes in patients with CLI. While limb salvage rates are similar, this analysis does not capture the frequency of re-interventions for either modality. Conte et al. (2009) showed in a meta-analysis of infra-inguinal surgical bypass procedures that only 61% of patients remain free from any amputation or re-intervention at one year. That number is significantly higher in the endovascular group (Conte et al., 2009).

It is important to note that limb salvage rates always surpass patency rates regardless of treatment modality. This is because revascularization allows patients to heal ischemic wounds and hopefully increase ambulation which will assist with collateral vessel development.

Table 2. Meta-analysis of 1-month to 3-year patency, limb salvage, and patient survival (%) in patients with critical limb ischemia comparing percutaneous transluminal angioplasty vs bypass grafting

Result	1 month	6 months	1 year	2 years	3 years
Primary patency					
PTA	77.4 ± 4.1	65.0 ± 7.0	58.1 ± 4.6	51.3 ± 6.6	48.6 ± 8.0
Bypass	93.3 ± 1.1	85.8 ± 2.1	81.5 ± 2.0	76.8 ± 2.3	72.3 ± 2.7
P	<.05	<.05	<.05	<.05	<.05
Secondary patency					
PTA	83.3 ± 1.4	73.8 ± 7.1	68.2 ± 5.9	63.5 ± 8.1	62.9 ± 11.0
Bypass	94.9 ± 1.0	89.3 ± 1.6	85.9 ± 1.9	81.6 ± 2.3	76.7 ± 2.9
P	<.05	<.05	<.05		
Limb salvage					
PTA	93.4 ± 2.3	88.2 ± 4.4	86.0 ± 2.7	83.8 ± 3.3	82.4 ± 3.4
Bypass	95.1 ± 1.2	90.9 ± 1.9	88.5 ± 2.2	85.2 ± 2.5	82.3 ± 3.0
Patient survival					
PTA	98.3 ± 0.7	92.3 ± 5.5	87.0 ± 2.1	74.3 ± 3.7	68.4 ± 5.5
Bypass	NA	NA	NA	NA	NA

Exercise and Peripheral arterial disease

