Exercise training is a proven effective treatment for patients with PAD with significant functional, psychosocial and economic benefits. In current practice, there are no guidelines for exercise training and rehabilitation for patients who have progressed to CLI and have undergone revascularization. While it may be a challenge given the severity of disease and number of comorbidities in this patient population, it is great a disservice to deny these patients exercise rehabilitation given the possible advantages for their functional capacity, quality of life and even survival. Randomized controlled trials (RCT) are necessary to determine the precise role of exercise rehabilitation in patients with CLI. An RCT will provide guidance for regarding exercise tolerance, appropriate exercise modalities as well as the challenges and benefits of exercise rehabilitation in this critically ill population.

Objectives:

The aim of this pilot study is to develop a better understanding of the role for supervised exercise rehabilitation programs (SEP) in CLI patients after revascularization.

Our key objectives are as follows:

- 1) Our primary objective is to show that a 12-week SEP will improve functional capacity and quality of life in patients with CLI after revascularization. We will assess the feasibility for completion of a 12-week SEP in patients with CLI who have undergone revascularization.
- 2) Our secondary objective is to monitor major adverse limb events (MALE) and survival in patients who complete a 12-week SEP after revascularization.

Hypotheses:

- 1) We hypothesize that PAD-CLI patients who participate in an exercise rehabilitation after they have undergone revascularization will have a greater improvement in functional capacity and quality of life compared with patients treated with best medical therapy alone.
- 2) We hypothesize that PAD-CLI patients who participate in an exercise rehabilitation after they have undergone revascularization will have fewer MALE and improved survival compared with patients treated with best medical therapy alone.

OUTCOME MEASURES:

Primary outcome measures:

Our primary outcome measure for this project will be change in functional capacity as measured by a 6-minute walking test (6MWT) or maximal pain-free walking distance on a treadmill.

Secondary outcome measures:

- 1) Quality of life based on questionnaires validated for patients with PAD, the SF-36 and VQ6
- 2) Completion of a 12 week supervised exercise program

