- 2) Freedom from MALE
- 3) Target vessel and/or bypass patency
- 4) Survival at 1, 3 and 5 years

STUDY DESIGN

This study is a two phase, single-center, non-blinded randomized controlled trial. The first phase of the trial will include 20 patients; 10 assigned to post-operative exercise rehabilitation and 10 to best medical therapy. The primary objective of Phase I is to assess for feasibility and safety of this randomized controlled trial in CLI patients after revascularization. We will assess rate of enrollment, adherence to the exercise regimen and any unforeseen barriers or challenges that patients may encounter with the rehabilitation program.

If Phase I of the trial confirms that the exercise program is feasible and safe for CLI patients post-revascularization, we will proceed with Phase II of the trial. The primary objective for Phase II is to determine if a supervised exercise rehabilitation program will improve walking distance after revascularization compared with patients treated with best medical therapy. Phase II will also compare quality of life outcomes between the two groups.

STUDY POPULATION

The population to be studied in this group is patients with PAD and CLI Fontaine classification III and IV. This means that these patients will have ischemic rest pain in their legs and/or non-healing ischemic ulcers on their feet.

ENROLLMENT

Patients will be identified on a referral basis through our outpatient vascular surgery clinic. The seven practicing vascular surgeons in Calgary will be informed of the current study. Patients who have undergone revascularization for CLI will be identified for consideration of participation in this study within six months of their procedure. All surgical and ischemic wounds to be deemed sufficiently healed prior to assessment for fitness in the study. Once the attending vascular surgeon considers the patient fit to participate, the research coordinator will assess the patient for possible inclusion in the study.

Inclusion Criteria

- 1) Ambulating prior to procedure
- 2) Living independently prior to procedure
- 3) Available to attend all SEP and follow-up appointments
- 4) PAD Fontaine class III and IV (rest pain and tissue loss)
- 5) Entry with consent of vascular surgeon
- 6) Ischemia secondary to TASC A-D lesions identified on imaging (CTA or angiogram)
- 7) Able to understand and sign informed consent
- 8) >18 years of age

Exclusion Criteria

- 1) Confined to wheelchair

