- 2) Patients with exercise tolerance limitations due to other co-morbidities such as cardiorespiratory, musculoskeletal, or peripheral neuropathy. (NYHA class III and IV)
- 3) PAD Fontaine class I and II (asymptomatic, claudication)
- 4) Patients with ongoing tissue loss that limits ambulation
- 5) Patient with previous revascularization procedures
- 6) Patients undergoing revascularization for acute limb ischemia events

SAMPLE SIZE

There are currently no data evaluating outcomes of post-revascularization supervised exercise programs in patients with critical limb ischemia, however these studies have been completed in claudication

patients. Studies on PAD claudication (Fontaine class II) patients who have undergone revascularization followed by SEP have all shown significant improvement in functional capacity compared with best medical therapy alone. These previous studies that showed consistently a 20% greater increase in walking distance in the post-revascularization SEP group compared with Best Medical Therapy (BMT) post-revascularization. Given this previous data, 64 patients are required to have a 80% chance of detecting, with a two-sided significance of 0.05, an increase in the primary outcome measure of a 20% greater increase in distance for the 6MWT in the experimental group compared with the control group. Final sample size will be adjusted for expected attrition.

METHODS

INTERVENTION

Patients included in the study will be identified in the vascular surgery outpatient clinic or through Emergency department as requiring revascularization secondary to critical limb ischemia. Patients will be approached regarding study participation prior to the revascularization procedure. After eligibility is confirmed and patients have signed informed consent, patients will be randomized to one of two groups:

- 1) Best Medical Therapy (BMT)
- 2) BMT + Supervised Exercise Program (SEP)

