The patient will undergo the revascularization procedure and any adjunctive treatment such as wound care/debridement or minor amputation (toes, trans-metatarsal amputation). All surgical wounds and ischemic ulcers will require assessment by attending surgeon for adequate healing prior to initial assessment at the exercise facility. This may require as little as one week or as long as 6 weeks to achieve sufficient healing. The exercise assessment and program delivery will take place at a cardiac rehabilitation facility that has extensive experience in managing patients with cardiovascular disease and PAD in the post op setting.

Best medical therapy

All patients in the study will be assessed and monitored by internal medicine specialists as well as the vascular surgery team for management of PAD risk factors including, but not limited to: hypertension, smoking cessation, dyslipidemia and diabetes. The patients will be prescribed appropriate pharmacotherapy as deemed appropriate. A typical regimen for these patients may include antiplatelet agents, B-blockers, ACE-inhibitors, and diabetic control agents. Patients will be advised to target a systolic blood pressure of $\leq 140\text{mmHg}$ ($\leq 130\text{mmHg}$ if diabetic), $\text{LDL-C} < 2.0\text{ mmol/L}$ and a $\text{HbA1c} \leq 7\%$. They will also be given information regarding engaging in exercise and physical activity three to five times per week. Patients will be asked to keep a log of their physical activity for the 12-week duration of the study. The patients will be provided with a log to record their physical activity.

Standardized Exercise Program Regimen

In addition to best medical therapy management, the patients randomized to the SEP arm of the trial will attend a supervised exercise program at a cardiac rehabilitation facility at least two times per week for 12 weeks. Programs will be designed and coordinated by an exercise physiologist. All patient expenses for the program will be covered by the study budget. There will be no financial burden placed on the participants.

MEASUREMENTS

General health metrics will be collected at the start and end of the 12-week intervention period. This includes height, weight, BMI, blood pressure and resting heart rate. We will record medications,

smoking history status, presence of diabetes, dyslipidemia, cardiovascular disease history including previous myocardial infarct (MI) and stroke/transient ischemic attack.

PRE/POST TESTING

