Microsoft Excel will be used to generate a block randomization sequence for Phase I (20 patients) followed by a block randomization sequence for Phase II (44 patients) of the study. Patients who are eligible to participate in the study will be stratified by sex and randomized to either SEP or BMT. Block sizes of 4 and 6 will be used to prevent anticipation of the randomization sequence.

ALLOCATION CONCEALMENT

Once the random block sequence has been generated, allocation cards will be created and sealed in sequentially numbered opaque envelopes. The envelopes will be stored in a secured filing cabinet in the vascular surgery research office. The envelopes will be opened sequentially after a patient consents to participate in the study.

DATA COLLECTION

No study data will be collected until patients have reviewed and signed the informed consent. Opportunity to ask questions and have time independent from study team will be provided.

Data will be recorded using Excel spreadsheets. Medical outcomes and complications will be tracked using Vascubase software. Data will be stored on Alberta Health Services computers to maintain patient confidentiality.

STATISTICAL ANALYSIS

Normally distributed data will be presented as mean \pm SD. Results at baseline and 12 weeks will be compared using a paired t-test. For data that is not normally distributed, comparisons will be performed using a non-parametric Mann-Whitney test. Comparisons will be accepted as statistically significant at 95% confidence level ($p \leq 0.05$). STATA software will be used for statistical analysis.

ETHICAL CONSIDERATIONS

Patients who are randomized to the SEP group will be provided with tri-weekly visits for supervised exercise guidance and support. Patients will receive reimbursement for travel to and from the exercise facility. This will include refunds for gas, parking or other required transportation (taxi, public transport, etc).

FOLLOW UP OF PATIENTS WITHDRAWN FROM STUDY

Patients who withdraw or do not complete the program will be contacted and interviewed at the end of the 12 week study period to understand why they were unable to complete the training program.

LIMITATIONS

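### The paired t-test named for the analysis cannot test the between-arm walking-distance hypothesis, and the 64 patients to be randomised include no allowance for attrition

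*Combined protocol and SAP*

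**What the plan says.** **The question.** Under Hypotheses, patients given exercise rehabilitation "will have a greater improvement in functional capacity and quality of life compared with patients treated with best medical therapy alone". Under Study Design, "The primary objective for Phase II is to determine if a supervised exercise rehabilitation program will improve walking distance after revascularization", again compared with best medical therapy (BMT).

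**The size.** Under Sample Size, "64 patients are required to have a 80% chance of detecting, with a two-sided significance of 0.05", for a 20% greater increase in six-minute walk test (6MWT) distance in the supervised exercise (SEP) arm than in the control arm. The section ends: "Final sample size will be adjusted for expected attrition".

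**The lists.** The Randomization section provides for a "block randomization sequence for Phase I (20 patients) followed by a block randomization sequence for Phase II (44 patients) of the study".

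**The test.** Under Statistical Analysis, for normally distributed data: "Results at baseline and 12 weeks will be compared using a paired t-test". For data that are not normal, a Mann-Whitney test is named. No other comparison is described, and none is identified as the primary analysis.

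**The outcome.** Outcome Measures gives the primary outcome as change in functional capacity by 6MWT or by pain-free treadmill distance. Sample Size uses the 6MWT only.

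**The concern.** The hypothesis and the sample size are about a difference between arms. The test named for normal data is about change over time. If the analysis section is followed as written, a normally distributed 6MWT result would give no estimate, confidence interval or p-value for SEP against BMT. The likely substitute is to compare one arm's p-value with the other's, which is not a valid test of a difference. All patients have just been revascularised, and BMT patients are also given advice on regular exercise, so improvement in both arms is plausible. Within-arm change therefore says little about SEP itself.

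The second matter is smaller. The 80% is tied to 64 patients before any loss, and the lists provide for exactly 64. The promised adjustment has no rate, no timing and no resulting total. The 64 is reached only by counting Phase I, whose stated objective is feasibility and safety, and no sentence says that the two phases are pooled for the walking-distance comparison.

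**Working it through.** **1. What each procedure tests.** Let D_S and D_B be the true mean changes in 6MWT distance from baseline to 12 weeks under SEP and BMT.

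| Item | Quantity concerned |
|---|---|
| Hypotheses; Sample Size | D_S − D_B |
| Paired t-test within SEP | D_S = 0 |
| Paired t-test within BMT | D_B = 0 |
| Paired t-test on all patients | average of D_S and D_B = 0 |
| Mann-Whitney on change, by arm | SEP against BMT |

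No paired test involves D_S − D_B. If D_S = D_B > 0, every paired test tends to significance as the sample grows, although SEP adds nothing.

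Comparing the two p-values does not repair this. As an illustration only, suppose both arms improve equally and each within-arm test has an assumed 80% power. The arms are independent, so exactly one test is significant with probability 2 × 0.80 × 0.20 = 0.32. About one time in three the arms would appear to differ when they do not.

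**2. Can the 64 be reproduced?** Not forward, because neither an SD nor a distance in metres is given. By the normal formula, n per arm = 2 × [(1.960 + 0.842) × SD / 20]². For a 20-point difference, the total is 50 at an assumed SD of 25 points, 72 at 30 and 126 at 40. The 64 is therefore neither confirmed nor refuted.

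**3. The effect implied by 64 for 80%.** Read 64 as the total, 32 per arm; 1:1 is stated for Phase I and assumed for Phase II. With two-sided alpha 0.05, the normal formula gives d = (1.960 + 0.842) × √(2/32) = 0.70. The two-sample t-test (noncentral t) gives d = 0.711. This is back-solved and is not the sponsor's figure.

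**4. The lists.** 20 + 44 = 64, the same as the number before attrition.

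**5. Power after loss.** Hold d = 0.711, pool both phases and assume equal loss in the two arms. The documents give no 12-week loss rate, so the rates below are assumptions. The last column is 64/(1 − loss), rounded up to an even number.

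| Loss | Evaluable of 64 | Power | Randomised to keep 64 evaluable |
|---|---|---|---|
| 0% | 64.0 | 80.0% | 64 |
| 5% | 60.8 | 77.9% | 68 |
| 10% | 57.6 | 75.6% | 72 |
| 15% | 54.4 | 73.1% | 76 |
| 20% | 51.2 | 70.4% | 80 |

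Check by the normal formula at 10% loss (28.8 per arm): 0.700 × √(28.8/2) − 1.960 = 0.70, which gives 75.7%.

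**The case against.** **On the test.** Mann-Whitney is an independent-groups test, and the hypothesis is explicitly comparative. A reader might infer that the sponsor plans no between-arm comparison at all; the documents do not support that. The more likely explanation is an incomplete section. What stands is that the test named for normal data is the wrong one and the primary comparison is not written down. It is also fair that ANCOVA is not the only valid choice: a two-sample comparison of change would test the hypothesis too.

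**On the lists.** A reader might infer an arithmetic error or a refusal to allow for loss. Neither is supported. The sum is correct, the adjustment is promised in the future tense, and Phase I is a natural place to learn about adherence and loss. This is an unfinished step. Any trial sized at exactly 80% falls below it with any loss, and at 5% the shortfall is about 2 points.

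**On pooling.** A reader might infer that Phase II is to be analysed alone, which would give about 64% power with 44 evaluable patients (22 per arm). That 20 and 44 sum exactly to 64 points to pooling as the intent. Only the statement is missing.

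**On the likely loss.** It is tempting to read a loss rate from Table 2, the "Meta-analysis of 1-month to 3-year patency, limb salvage, and patient survival (%) in patients with critical limb ischemia". The documents do not support this. The Intervention section randomises before the procedure, but Enrollment identifies patients after it, once wounds have healed and the surgeon considers them fit. In the second order, early deaths and amputations precede randomisation and are not trial attrition. Even in the first order, 1 to 6 weeks of healing plus 12 weeks puts the test at 13 to 18 weeks, between the table's 1-month and 6-month columns.

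**On pilot status.** The documents call the trial a pilot. They also make a formal power claim and give Phase II an efficacy objective, so both should be stated correctly.

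**Conclusion.** The main point holds. As written, the analysis for normally distributed data does not address the trial's own hypothesis, and no sample size would change that. It is easily corrected before analysis.

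The secondary point holds as an incompleteness. With 64 randomised and both phases pooled, the 80% claim requires no loss before the 12-week test. Power is about 78% to 70% at assumed losses of 5% to 20%. These figures rest on the protocol's own 64 for 80%, which cannot be checked without an SD, and on a two-sample t-test, 1:1 allocation and equal loss in the arms. No loss rate can be drawn from the documents, so the size of the shortfall is the sponsor's to state.

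**What to change.** **Statistical Analysis.** Name one primary analysis, fixed before data are analysed: a between-arm ANCOVA of 12-week 6MWT distance adjusted for baseline 6MWT, reported as the SEP minus BMT difference with a 95% confidence interval. If Mann-Whitney is kept as the alternative, say that it compares the arms. Keep paired tests as descriptive only. The 6MWT is already planned at both times, so no patients or measurements are added (this assumes that BMT patients have both tests). Claim no recovered power, since the baseline-to-12-week correlation and the SD behind the 64 are not given.

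**Outcome Measures.** Reconcile the either-or primary outcome with the 6MWT used in Sample Size.

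**Sample Size and Randomization.** State that Phase I and Phase II patients are pooled for the walking-distance comparison, and give the SD and distance behind the 64. Reconcile Enrollment and Intervention on when randomisation takes place, so that loss can be defined. Then choose one:

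- Replace the sentence promising adjustment with: *64 randomised patients (20 and 44, pooled) give 80% power with no loss before the 12-week 6MWT, and [y]% at our expected loss of [x]%.* The cost is wording and a slightly lower stated power.
- Mark the Phase II number of 44 as provisional, to be reset to 64/(1 − x) − 20 at expected loss x. The cost is wording now and, at 5, 10, 15 or 20% loss, 4, 8, 12 or 16 more patients later (a Phase II list of 48, 52, 56 or 60). Do not rest x on Phase I alone: 2 lost of 20 is 10%, with an exact 95% confidence interval of 1% to 32%.

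### The protocol gives two incompatible entry sequences; in one, as written, randomization precedes surgery, so healing clearance and the baseline walk follow a known allocation

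*Combined protocol and SAP*

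**What the plan says.** Two sections describe how a patient enters the trial.

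- **Enrollment:** "Patients who have undergone revascularization for CLI will be identified for consideration of participation in this study within six months of their procedure". Wounds must have healed before fitness is considered, and then "Once the attending vascular surgeon considers the patient fit to participate, the research coordinator will assess the patient for possible inclusion in the study".
- **Methods, Intervention:** patients are identified in clinic or the emergency department while they still need the operation. "Patients will be approached regarding study participation prior to the revascularization procedure". Next, "After eligibility is confirmed and patients have signed informed consent, patients will be randomized to one of two groups". The text then continues: "The patient will undergo the revascularization procedure and any adjunctive treatment such as wound care/debridement or minor amputation", followed by "All surgical wounds and ischemic ulcers will require assessment by attending surgeon for adequate healing prior to initial assessment at the exercise facility". Healing is expected to take one to six weeks.

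Four other places bear on the point.

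- **Allocation Concealment** ties opening of the envelope to consent and to nothing later.
- **Study Design:** "This study is a two phase, single-center, non-blinded randomized controlled trial".
- **Pre/Post Testing, Functional Capacity** places the baseline walk at the opening exercise session. Under Standardized Exercise Program Regimen, "the patients randomized to the SEP arm of the trial will attend a supervised exercise program at a cardiac rehabilitation facility"; no such attendance is described for the control arm.
- **Outcome Measures** defines the primary outcome as a change in functional capacity.

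**The concern.** Staff cannot follow both sequences. One screens after surgery and healing; the other approaches patients before surgery and, in the order written, randomizes them then too. When to screen, open the envelope and test baseline is therefore undetermined.

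The choice has consequences.

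- **Bias.** If allocation is known before clearance and baseline, it can influence who reaches baseline, when in recovery they are tested and how hard they try. A patient who is never cleared has no change score, so the primary analysis cannot include that patient without further assumptions.
- **Population.** The exclusion for tissue loss that limits walking can be answered differently before surgery and after healing.
- **Phase I feasibility.** Enrollment and adherence rates have different denominators under the two sequences, and feasibility is what Phase I is meant to assess.

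**Working it through.** **1. The two sequences side by side**

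| Step | Enrollment | Intervention, in the order written |
|---|---|---|
| Patient when identified | Already revascularized, up to six months earlier | Still needs revascularization |
| Wound healing | Before screening | After randomization and surgery |
| Surgeon's clearance | Before screening | After randomization and surgery |
| Eligibility, consent | After clearance | Before surgery |
| Randomization | Not placed | After consent, written before surgery |

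For one patient, screening cannot both follow healing and precede the operation. That conflict stands wherever randomization falls. Even under the Enrollment order, the baseline walk would precede allocation only if testing were placed before the envelope is opened, and no section says so.

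**2. The plan's own sample size**

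Sample Size gives 64 patients, 80% power and a two-sided 0.05 level; the Randomization section's 20 + 44 = 64 confirms the total. No SD is given, so the figure can only be worked backwards. With 32 per arm, a two-sample t-test has 80% power for a difference of 0.711 SD.

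**3. Illustration of selective loss before baseline (all inputs assumed)**

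Let fitness be standard normal, and let the least fit fraction q of an arm never reach baseline. The mean fitness of those remaining is φ(z_q)/(1 − q):

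- q = 5%: 0.109
- q = 10%: 0.195
- q = 15%: 0.274
- q = 20%: 0.350

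Multiplying the difference between arms by the correlation r between fitness and change gives the spurious difference in change, in SD units.

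| Loss, SEP vs BMT | Fitness gap | r = 0.3 | r = 0.5 |
|---|---|---|---|
| 10% vs 5% | 0.086 | 0.026 | 0.043 |
| 15% vs 5% | 0.166 | 0.050 | 0.083 |
| 20% vs 5% | 0.241 | 0.072 | 0.121 |

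For the middle row, 0.050/0.711 = 7% and 0.083/0.711 = 12% of the detectable difference. With r = 0 the bias is zero; with negative r it reverses sign.

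**4. Loss that is equal in both arms (costs power only)**

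Table 2 of the protocol gives one-month figures for critical limb ischemia.

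- Angioplasty: limb salvage 93.4% and survival 98.3%. Assuming independence, 1 − 0.934 × 0.983 = 8.2% lost, leaving 32 × 0.918 = 29.4 per arm and power of 76.4%.
- Bypass: limb salvage 95.1%, survival not available. Then 1 − 0.951 = 4.9% lost, leaving 30.4 per arm and power of 77.9%.

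These apply only if the promised attrition adjustment, for which no rate is given, does not already cover such losses.

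**The case against.** The strongest reply is that no sentence says patients are randomized before surgery. Randomization waits for confirmed eligibility, Enrollment places inclusion screening after healing and clearance, and entry requires the surgeon's agreement. The criteria on walking and living independently before the procedure also read naturally as a look back. An early approach, with eligibility and randomization after healing, therefore has support in the text. This reading is fair but is stated nowhere. The Intervention section puts surgery and healing after the randomization sentence, and the envelope is tied only to consent. It also leaves the clash between already operated and still awaiting operation untouched.

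The second reply is that the bias is conditional and small. A non-blinded design does not establish that the surgeon is told the arm, the healing check covers every patient, and no figure in the document supports the assumed losses or correlations. With 32 per arm, the 15% versus 5% case raises the two-sided false-positive rate from 5% to only about 5.4% to 6.2%, and the most extreme case (0.121 SD) to 7.6%. This stands, with the limit that the illustration covers selective loss only; differences in test timing and effort are not quantified.

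Third, the one-to-six-week healing range is clinical variation under either sequence, and equal loss is a power question. Both are side points. The control arm's baseline occasion is unclear rather than missing, since other sections mention an initial assessment and first and final visits.

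Finally, later randomization leaves events around the procedure outside the randomized comparison. That is true, but it fits hypotheses about exercise after revascularization.

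**Conclusion.** The concern holds and needs correcting before enrollment. The contradiction between Enrollment and Intervention is certain and rests on the text alone. That randomization precedes surgery is an inference from the written order. If it is followed, clearance and baseline come after the envelope is opened in an open trial with a change-score outcome.

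The document shows a route to bias but not its size. Under the assumed losses and correlations the spurious difference runs from 0.03 to 0.12 SD, against a detectable 0.71 SD. The case for correction does not depend on those values: the entry procedure cannot be carried out as written, and patients randomized before baseline cannot afterwards be given a pre-allocation baseline.

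**What to change.** Rewrite Enrollment, Intervention and Allocation Concealment as one sequence.

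1. Consent may be taken before the procedure.
2. Open the envelope only after the surgeon's clearance, a final eligibility check and the baseline assessment (6MWT, treadmill test, quality of life, ABI), done the same way in both arms.
3. In Pre/Post Testing, replace the reference to the opening exercise session with a pre-randomization baseline assessment.
4. Start the 12-week period at the same point in both arms, and analyse all randomized patients in their assigned groups.
5. Report Phase I counts at each step (approached, consented, cleared, randomized) so that the feasibility denominators are explicit.

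The timing and criteria of clinical clearance stay with the investigators; the passages describing them need only be made consistent.

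The cost is protocol wording and a later envelope opening. Control patients need a defined baseline assessment, which a change outcome already requires. Patients learn their arm later, exercise places are booked later, and events before randomization fall outside the comparison, which the protocol should say.
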